## 11.0 REPORTING ADVERSE EVENTS AND PROTOCOL DEVIATIONS

All AEs meeting DAIDS grade 3 severity or above including local and systemic reactions not meeting the criteria for SAEs will be captured. Information to be collected includes event description, time of onset, clinician's assessment of severity, relationship to study product (assessed only by those with the training and authority to make a diagnosis), and time of resolution/stabilization of the event. All AEs meeting DAIDS grade 3 severity or above occurring while on study must be documented appropriately regardless of relationship. All AEs meeting DAIDS grade 3 severity or above will be followed to adequate resolution.

Any medical condition (including a laboratory abnormality) that is present at the time that the participant is screened will be considered as baseline and not reported as an AE. However, if the study participant's condition deteriorates at any time during the study, it will be recorded as an AE.

Changes in the severity of an AE will be documented to allow an assessment of the duration of the event at each level of severity to be performed. AEs characterized as intermittent require documentation of onset and duration of each episode.

AEs meeting DAIDS grade 3 severity or above must be recorded into the case report forms and will be reported per the following guidelines (**Error! Reference source not found.2**).

It is the responsibility of the principal investigator to use continuous vigilance to prevent, identify and report protocol deviations. Major protocol deviations must be reported to the UVA IRB-HSR per the following guidelines (Table 2). Minor deviations do not need to be reported to the UVA IRB-HSR. All deviations must be addressed in study source documents.

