2.0 Outcomes

2.1 Primary outcome: The primary efficacy endpoint of this double-blind, placebo-controlled phase IIa trial is a binary indicator for whether a patient would be alive and free of invasive mechanical ventilation at 28 days. The outcome will be summarized as the proportion of patients alive and free of invasive mechanical ventilation at 28 days in those receiving dupilumab in addition to standard of care (treatment arm) compared to those receiving solely standard of care management (placebo arm).

2.2 Secondary outcomes:

2.2.1 Eosinophilia as the safety outcome: The safety endpoint of this study is a binary indicator for whether a patient would have eosinophilia, which is defined as an absolute eosinophil count $> 0.6 \text{ k}/\mu\text{l}$ at ≥ 1 measurement throughout the study period. The outcome will be summarized as the proportion of patients with eosinophilia for treatment arm and placebo arm respectively. Complete blood counts with differentials

and complete metabolic panels will be measured on Day 0, 2, 5, 7, 14, 28 and 60. Day 7, 28 and 60 optional, although recommended, if patient discharged within the time frame.

2.2.2 **Other secondary safety and efficacy outcomes:**

- Cumulative incidence (defined as number of new events divided by the total number of individuals in the population at risk for the time interval) of grade 3 and 4 adverse events, serious adverse events or death including: injection site reactions, eye/eyelid inflammation, conjunctivitis, oropharyngeal pain, insomnia, tooth ache, gastritis, arthralgia, bacterial pneumonia, herpes viral infection, hypereosinophilic syndrome, hypersensitivity reaction.
- Prevalence of B.1.1.7 and B.1.351 and other SARS-CoV-2 lineages in study cohort: Day 0.
- Plasma total Immunoglobulin E (IgE) levels: Day 0 and 14.
- Plasma inflammatory markers (C-reactive protein and ferritin): Day 0, 7 and 14. Day 7 optional if patient discharged.
- Plasma cytokine levels including TARC (CCL17), YKL40, eotaxin 3 (CCL26), IL-13, IL-4, Arg1, Hyaluronan, soluble ST2: Day 0, 2, 5, 7, 14, and 28. Day 7 and 28 optional if patient discharged.
- Change in PaO₂/SaO₂ to FiO₂ ratio: Day 0, 2, 5, 7 (if patient remains inpatient throughout)
- All-cause mortality rate at 28 days.
- Hospital length of stay (LOS)
- ICU LOS
- Proportion of patients alive and free of invasive respiratory failure at 28 days.
- Proportion of patients alive and free of invasive mechanical ventilation at 60 days.

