5.3 Secondary outcomes

5.3.1 Eosinophilia as the safety outcome: Eosinophilia is a binary indicator for a patient

to have an absolute eosinophil count $> 0.6 \text{ k}/\mu\text{l}$ at ≥ 1 measurement based on the blood counts with differentials and complete metabolic panels on Day 0, 2, 5, 7, 14, 28 and 60 (Data on Day 7, 28 and 60 would be optional). The outcome will be summarized as the proportion of patients with eosinophilia and the difference in the proportions between the two study arms will be evaluated with Chi-square test. The odds ratio of having eosinophilia for Dupilumab vs. placebo and its 95% CI will also be estimated in logistic regression, with adjustment for other covariates.

5.3.2 Other secondary safety and efficacy outcomes:

- Cumulative incidence rate of adverse events (injection site reactions, eye/eyelid inflammation, conjunctivitis, oropharyngeal pain, insomnia, tooth ache, gastritis, arthralgia, bacterial pneumonia, herpes viral infection, hypereosinophilic syndrome, hypersensitivity reaction, other grade 3 or 4 adverse events, serious adverse events or death) is defined as number of adverse events divided by the total number of individuals in the population at risk for the time interval. The rate ratio of adverse events for Dupilumab vs. placebo and its 95% CI will be analyzed in Poisson regression, in which the follow-up time interval will be considered as the offset. Adjusted analysis for other covariates will be performed, as necessary. Mortality at 60 days will be analyzed as the time to event response. Survival probabilities will be estimated by the Kaplan-Meier method, and the difference in the mortality risk between the two treatment groups will be evaluated by the log-rank test and further in Cox regression, adjusting for the baseline covariates. For the analysis of mortality over the first year, additional adjustment for dynamic mechanical ventilation effect will be considered by including being on ventilation as a time-vary covariate in the Cox regression.
- Plasma total Immunoglobulin E (IgE) levels on Day 0 and 14 will be considered as continuous responses, and difference between treatment arms will be evaluated by t-test or Wilcoxon test initially, and adjusted difference and its 95% CI will be estimated from linear regression. Further, changes of IgE from Day 0 to Day 14 will also be explored and the difference between the two study arms will be analyzed similarly.

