- Plasma inflammatory markers (C-reactive protein and ferritin) on Day 0, 7 and 14 (Day 7 would be optional if patient discharged) will be analyzed as longitudinal responses in the linear mixed effects model with Dupilumab treatment as a fixed effect. Since this is a randomized study, significant effect of treatment on intercept is not expected. Thus, the longitudinal analysis will focus on the slope difference between the treatment arms via interaction of treatment and time in the model. Since there are only 3 measures for each subject, only random slopes will be specified as *a priori*. Model fitting indices will be examined carefully to ensure the validity of estimated parameters. If Day 7 data won't be available for all patients, these biomarkers between Day 0 to Day 14 will be analyzed as the IgE above.
- Plasma cytokine levels including TARC (CCL17), YKL40, eotaxin 3 (CCL26), IL-13, IL-4, Arg 1, Hyaluronan, soluble ST2 on Day 0, 2, 5, 7, 14, and 28 (Day 7 and 28 optional if patient discharged) will be analyzed as longitudinal responses

in the linear mixed effects model with Dupilumab treatment as a fixed effect, and with appropriate transformation of biomarkers if necessary. The trajectories of these biomarkers will be carefully evaluated, and the slope difference between the treatment arms will be evaluated by the interaction of treatment and time.

Additional curvature in trajectories will also be explored and captured whenever possible in the linear mixed effects model.

- Change in $\text{PaO}_2/\text{SaO}_2$ to FiO_2 ratio on Day 0, 2, 5, 7 (if patient remains inpatient throughout) will be analyzed as longitudinal responses in the linear mixed effects model, similar methods to that for inflammatory biomarkers and cytokine biomarkers as described above.
- All-cause mortality at 28 days will be analyzed as the binary response, using the same methods as that for the primary efficacy outcome and eosinophilia.
- Hospital length of stay (LOS) and ICU LOS between treatment arms will be analyzed as continuous measures using t-test or Wilcoxon test initially, and adjusted difference and its 95% CI will be estimated from linear regression. Since the distributions of hospital LOS and ICU LOS are often skewed, the log-transformed LOS data will be considered in the analyses.
- The response of being alive and free respiratory failure at 28 days is a binary response and will be analyzed using the same methods as that for the primary efficacy outcome.

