- The response of being alive and free invasive mechanical ventilation at 60 days is a binary response and will be analyzed using the same methods as that for the primary efficacy outcome.
- National Institute of Allergy and Infectious Diseases (NIAID) 8-point ordinal scale on Day 0, 2, 5, 7, 14, 28, 60, 180 and 360 will be considered as longitudinal data. The distributions of the data will be examined visually first and further collapsing will be considered. Collapsed data will be analyzed in the generalized linear mixed effect model or multinomial logistic regression with the generalized estimating equation approach.
- Proportion of patients alive and free of invasive mechanical ventilation at 60, 90, 120, 150, 180, 270 and 360 days will be estimated from the Kaplan-Meier survival for the time to mechanical ventilation-free survival over the first year. The difference in these proportions between the two treatment groups will be evaluated by the log-rank test and further in Cox regression adjusting for the baseline covariates. For the analysis of mortality over the first year, additional adjustment for dynamic mechanical ventilation effect will be considered by including being on ventilation as a time-vary covariate in the Cox regression.
- Need for vasopressors is a binary response and will be analyzed using the same methods as for the primary efficacy outcome.
- Need for renal replacement therapy is a binary response and will be analyzed using the same methods as for the primary efficacy outcome.
- Need for extracorporeal membrane oxygenation (ECMO) is a binary response and will be analyzed using the same methods as for the primary efficacy outcome.

6.0 Other safety analyses:

Analysis of adverse event (AE) data will primarily be descriptive based on CTCAE coding of events. The proportion of subjects experiencing a severe AE and the proportion experiencing a Grade 3 or higher will be recorded. AE will be compared to published data.

7.0 Sample size estimation and power analysis:

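### The single adverse-event rate ratio in SAP 5.3.2 mixes drug reactions with deaths and serious events that the drug may prevent, so it can dilute or offset an excess of reactions

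*SAP*

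**What the plan says.** SAP 5.3.2, first bullet, defines a cumulative incidence rate of adverse events. The list in brackets holds 12 named reactions, from injection site reactions to hypersensitivity, and ends with "other grade 3 or 4 adverse events, serious adverse events or death) is defined as number of adverse events", divided by the number of individuals at risk. The analysis is given in the singular: "The rate ratio of adverse events for Dupilumab vs. placebo and its 95% CI will be analyzed in Poisson regression", with the follow-up interval as offset. Neither deaths nor events due to COVID-19 are excluded.

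SAP 2.2.2 defines the same outcome differently, as "grade 3 and 4 adverse events, serious adverse events or death including: injection site reactions" and so on. There the named reactions are examples of severe, serious or fatal events. In 5.3.2 they stand beside other grade 3-4 events.

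Some components are also analysed alone. "Mortality at 60 days will be analyzed as the time to event response", and "All-cause mortality at 28 days will be analyzed as the binary response". For eosinophilia, "The odds ratio of having eosinophilia for Dupilumab vs. placebo and its 95% CI will also be estimated in logistic regression". Vasopressors, renal replacement and ECMO each have their own binary analysis.

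SAP 6.0 makes the remaining adverse-event analysis primarily descriptive by coded event, and adds: "The proportion of subjects experiencing a severe AE and the proportion experiencing a Grade 3 or higher will be recorded". The only comparison it names is with published data. It does not list the proportion of patients with a serious event.

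**The concern.** A safety ratio should answer whether the drug causes more reactions. This count combines two kinds of event on which an effective drug may act in opposite directions: reactions it may cause, and deaths and serious events it is meant to prevent. Death, and death or invasive ventilation combined, appear among the SAP's efficacy outcomes (2.1 and 2.2.2). If the drug works, the second kind falls in the dupilumab arm and pulls the pooled ratio down, whatever happens to the first.

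At stake is the interpretation of the only between-arm model that covers conjunctivitis, herpes infection, hypersensitivity and the other named reactions. A pooled ratio near 1 could mean no excess of reactions, or an excess offset by benefit. The trial is meant to inform later trials, so an estimate that blends efficacy with harm is a poor thing to carry forward.

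**Working it through.** **Inputs from the documents.** 20 patients per arm (40 randomised 1:1, SAP 1.2). Alive and ventilator-free at 28 days: 79.5% under usual care and 97.2% on dupilumab (SAP 7.0). 7 of 40 patients died by Day 60, split by arm not given (protocol 6.2).

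**Inputs that must be assumed.** Background named reactions per arm, S0 = 2, 4, 6 or 10. One recorded adverse event per failure (death or ventilation). Equal follow-up. The documents give no adverse-event rates.

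**Step 1, the plan's own figure.** SAP 7.0 states 75% power for 79.5% against 97.2%, score test, one-sided alpha 0.10. Exact binomial enumeration of that test with 20 per arm gives 75.1%, so these rates are a sound base.

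**Step 2, failures per arm.** Placebo: 20 × (1 − 0.795) = 4.1. Dupilumab: 20 × (1 − 0.972) = 0.56. Gap: 3.54.

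**Step 3, pooled ratio.** With a true reaction ratio R, the pooled ratio is (R × S0 + 0.56) / (S0 + 4.1). If the drug has no clinical benefit, 4.1 replaces 0.56.

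| S0 | R = 2, SAP's benefit | R = 2, no benefit | R = 3, SAP's benefit |
|---|---|---|---|
| 2 | 4.56/6.1 = 0.75 | 8.1/6.1 = 1.33 | 6.56/6.1 = 1.08 |
| 4 | 8.56/8.1 = 1.06 | 12.1/8.1 = 1.49 | 12.56/8.1 = 1.55 |
| 6 | 12.56/10.1 = 1.24 | 16.1/10.1 = 1.59 | 18.56/10.1 = 1.84 |
| 10 | 20.56/14.1 = 1.46 | 24.1/14.1 = 1.71 | 30.56/14.1 = 2.17 |

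The pooled ratio equals exactly 1 when R = 1 + 3.54/S0, that is at R = 2.77, 1.89, 1.59 and 1.35 for the four values of S0. If each failure generates two recorded events, the gap doubles and these become 4.54, 2.77, 2.18 and 1.71.

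**Step 4, deaths alone.** Deaths are in the count by the text itself. Take the 7 deaths, assume a dupilumab:placebo split between 1:6 and 3:4, with S0 = 4 and R = 2. The pooled ratio runs from (8 + 1)/(4 + 6) = 0.90 to (8 + 3)/(4 + 4) = 1.38.

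**Step 5, chance of seeing the excess.** The probability that the 95% CI lies wholly above 1 comes from Poisson enumeration with a Wald interval on the log ratio (0.5 added to both counts when either is zero), for R = 2.

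| Named events, placebo vs dupilumab | Named events alone | Pooled count |
|---|---|---|
| 4 vs 8 | 14% | 2.5% |
| 6 vs 12 | 26% | 6.5% |

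Pooling lowers the chance in both rows, but it is low either way.

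**The case against.** A reader might infer that clinical benefit cancels drug harm, so that a harmful signal will read as no difference. The documents do not support that as a general statement, for five reasons.

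- Full cancellation is one scenario. It needs real benefit and an excess of reactions close to the number of failures prevented. With no benefit the signal is diluted but stays above 1, and a true tripling still gives 1.08 to 2.17.
- Harm can show elsewhere. Eosinophilia, the lead safety outcome, has its own test and odds ratio, mortality is analysed separately, and an excess of one reaction should be visible in the coded-event tables of SAP 6.0.
- Pooling is the natural reading but not an explicit statement. The wording does not exclude one ratio per category.
- Capture of COVID-driven serious events is inferred. The supplied protocol says that all grade 3 or higher events "including local and systemic reactions not meeting the criteria for SAEs will be captured" (section 11.0), but it governs the one-year extension. The parent trial's protocol, to which this SAP belongs, is not supplied. Only deaths are certain to be in the count.
- Small numbers are the larger reason for an inconclusive result, and the outcome is secondary in a trial the SAP calls exploratory.

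All five stand, and they limit the size of the point. They do not remove it. None of the other analyses gives a between-arm estimate for the named reactions. Low power widens the interval, whereas pooling moves the estimate itself, and a larger trial would not cure that. If ratios by category were intended, the SAP should say so.

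**Conclusion.** The point holds in a limited form. Read naturally, SAP 5.3.2 yields one ratio that cannot separate harm from benefit, and it is the only between-arm model planned for the named reactions. Under the SAP's own assumed benefit, a doubling of reactions would appear as roughly 0.75 to 1.46, depending on the background count. The result rests on three assumptions that the documents do not settle: 2 to 10 background reactions per arm, one recorded event per death or ventilation, and equal follow-up. The accurate wording is that pooling can dilute or offset an excess of reactions, not that it hides one.

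The mismatch between SAP 2.2.2 and 5.3.2 over which named reactions count needs no assumption and should be reconciled in any case. Priority is low to moderate.

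**What to change.** In SAP 5.3.2, replace the single count with:

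- (a) a rate ratio for the 12 named reactions, with the number of patients having each reaction by arm;
- (b) a rate ratio for serious and other grade 3-4 events, excluding death and invasive ventilation.

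Leave deaths to the mortality analyses already planned. Keep any pooled rate as a descriptive supplement.

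Reconcile 2.2.2 with 5.3.2: state whether a named reaction counts at any grade or only when it is grade 3-4, serious or fatal. In 6.0, add the proportion of patients with at least one serious adverse event, by arm.

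The cost is SAP wording and a few table rows. The statistical price is fewer events behind each ratio, hence wider confidence intervals.

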3.0 General considerations

3.1 Analysis populations: Each primary and secondary efficacy outcome measure will be analyzed for the intent-to-treat (ITT) and evaluable population. The intent-to-treat principle is that participants will be analyzed in the groups to which they were randomized, regardless of whether they received the randomized study medication. Another analysis population of interest is the as-treated population. The as-treated population will consist of only participants who were inducted onto study medication, even one dose of drug. Safety outcome will be primarily analyzed for the as-treated population.

Major differences in the results for the ITT and as-treated populations, if any, will be further explored. While there is every intention to be complete in describing the analyses to be performed, it is not possible to anticipate every contingency, and some adjustments may be required to meet constraints posed by the structure of the data. Constraints such as non-linearity, non-normality, etc. may lead to different but more appropriate approaches to analysis.

3.2 Testing of Distribution assumptions: Empirical distributions of all variables will be visually inspected to detect outliers. The underlying proposed statistical methods for each analysis will be examined, primarily through inspection of graphical displays, standardized residuals, or influence diagnostics. Where appropriate and/or necessary, transformations will be utilized for continuous measures such as biomarker data, or categorized biomarkers will be analyzed.

3.3 Interim analysis: there is no formal scheduled interim analysis with respect to the primary efficacy outcome and thus the sample size estimation would not be altered. However, analysis for some selected biomarkers will be performed after the 14th day of the 20th patient enrolled. Particularly, the proportion and rate of change of C- reactive protein and ferritin levels will be calculated from day 0 and day 14 time points to determine efficacy trends between the two treatment groups. Additionally, percentage of eosinophilia will be calculated between the two groups to determine safety trend. Data will be analyzed by a third party and remain blinded to the study investigators. We expect greater changes in C-reactive protein and ferritin for patients receiving Dupilumab than those receiving placebo and no significant differences in eosinophilia between the two groups.

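### The adverse event rate ratio comes from plain Poisson regression with no counting rule for repeat events and no allowance for variation between patients, so its 95% CI can be too narrow or too wide

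*SAP*

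**What the plan says.** SAP 2.2.2 lists the outcome as a cumulative incidence, meaning "number of new events divided by the total number of individuals in the population at risk for the time interval". SAP 5.3.2 calls it a cumulative incidence rate and says it "is defined as number of adverse events divided by the total number of individuals in the population at risk for the time interval". Dupilumab is compared with placebo by a rate ratio with a 95% confidence interval, which "will be analyzed in Poisson regression, in which the follow-up time interval will be considered as the offset".

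On covariates, 5.3.2 says only: "Adjusted analysis for other covariates will be performed, as necessary". No scale parameter, robust variance, negative binomial model or rule for repeat events appears there.

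Two general provisions apply to all analyses. SAP 3.2 says: "The underlying proposed statistical methods for each analysis will be examined, primarily through inspection of graphical displays, standardized residuals, or influence diagnostics". SAP 3.1 adds that constraints in the data "may lead to different but more appropriate approaches to analysis". SAP 6.0 makes adverse event reporting mainly descriptive and records the proportion of subjects with a severe event and with a Grade 3 or higher event.

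All of this concerns the 40-patient parent trial. The one-year extension protocol does not specify the Poisson analysis.

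**The concern.** Three quantities are being run together. Events divided by individuals is a mean count per person, which can exceed 1. A cumulative incidence is the proportion of patients with at least one event. A Poisson model with a follow-up offset estimates events per unit of person-time. A reader of the results could not tell which one was compared.

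The variance is the second issue. Poisson regression sets the variance of a patient's count equal to its mean. If some patients are prone to many events and others to none, the variance is larger and the model-based interval is too short.

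The documents make unequal risk plausible. SAP 1.4 stratifies on oxygen need because severity may affect outcomes. The eligibility criteria admit transplant, immunodeficient, cancer and renal failure patients. Protocol 6.2 reports 7 of 40 dead by Day 60. The event list also overlaps: one bacterial pneumonia could be counted again as a serious adverse event and again as a death, and nothing prevents this.

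At stake is a spurious safety difference, or false reassurance from an interval of the wrong width, in a trial whose stated emphasis (SAP 7.0) is exploratory estimation.

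**Working it through.** **Inputs from the documents.** 40 patients randomized 1:1, so 20 per arm (SAP 1.2); follow-up to 60 days (SAP 1.2); 7 of 40 dead by Day 60 (Protocol 6.2); two-sided 5% tests (SAP 3.4). The documents give no figure for the adverse event analysis to reproduce. The only computed design figure is 75% power for the primary endpoint. An exact score test gives 75.1%, and it has no bearing on this point.

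**Assumed inputs.** The documents give neither event rates nor dispersion. Assumed here: a mean of 0.5 to 3 events per patient over 60 days, and gamma patient frailty with variance 0 to 2.

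**Step 1: formula when repeat events count.** With E₁ and E₀ events in the two arms, the Poisson standard error of the log rate ratio is √(1/E₁ + 1/E₀). With mean μ and frailty variance d, the variance is inflated by φ = 1 + μd. The true standard error is √φ times the Poisson one, and coverage of the nominal 95% CI is 2Φ(1.96/√φ) − 1.

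| φ | √φ | Coverage |
|---|---|---|
| 1 | 1.00 | 95% |
| 1.5 | 1.22 | 89% |
| 2 | 1.41 | 83% |
| 3 | 1.73 | 74% |

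Example, ignoring deaths: μ = 1 and d = 1 give 20 events per arm and φ = 2. The Poisson standard error is √(2/20) = 0.316, so at an observed ratio of 1 the CI is exp(±1.96 × 0.316) = 0.54 to 1.86. The true standard error is 0.316 × 1.414 = 0.447, and the CI should be about 0.42 to 2.40.

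**Step 2: simulation.** 20 per arm, true rate ratio 1, each patient dying with probability 7/40 at a uniform time, 40,000 replicates; the 0.25 row is from separate runs. False rejection by the plain Poisson interval:

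| Frailty variance | 0.5 events per patient | 1 event | 2 events |
|---|---|---|---|
| 0 | 3% | 4% | 5% |
| 0.25 | 5% | 7% | 10–11% |
| 0.5 | 6% | 10% | 16% |
| 1 | 8% | 15% | 25% |
| 2 | 13% | 24% | 37% |

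At 0.25 events per patient, as might hold for a single event type, rejection is about 5% or less even at variance 2.

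**Step 3: the same data with an adjusted variance.** A patient-level robust or Pearson-scaled variance with a t reference (2 × 20 − 2 = 38 degrees of freedom) gives coverage of 93% to 97% in every setting with 0.5 to 3 events. The median Pearson-scaled interval is 1.0 to 2.0 times as wide as the Poisson one at 0.5 to 2 events per patient, and up to 2.4 times at 3 events with variance 2.

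**Step 4: if only first events count.** Each patient then contributes 0 or 1. With the whole follow-up interval as offset, the true variance is (1 − p) times the Poisson variance, where p is the patient's risk. For p = 0.1 to 0.5 the ratio is 0.9 to 0.5. At p = 0.3, coverage is 2Φ(1.96/√0.7) − 1 = 98%; over the range it is 96% to 99%. Simulated rejection at 20 per arm is below 1%. The interval is too wide.

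**The case against.** The strongest reply is that the harm is unproven. No event count or dispersion is given, and the wording in SAP 2.2.2 can be read as first events only, which reverses the error. This stands. A reader might infer that the intervals are certainly too narrow, or that a false safety finding is likely. The documents support neither.

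A second reply is that the SAP already protects itself through model checking, freedom to change method, cautious interpretation of multiple tests, and a proof-of-concept aim. This stands in part and lowers the stakes. But the diagnostics text does not name overdispersion and gives no decision rule. Elsewhere the SAP handles repeated data on the same patient explicitly, with mixed models for biomarkers and generalized estimating equations for the ordinal scale; here it does not.

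A third reply is that patient-level proportions are planned in SAP 6.0. They are to be recorded and adverse events compared with published data, but no between-arm estimate is specified.

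Two stronger readings fail. A reader might take the Poisson ratio as the only between-arm safety comparison. It is not: eosinophilia has a Chi-square test and odds ratio, and death has log-rank, Cox and 28-day binary analyses. A reader might also think the offset is entered on the wrong scale. Naming follow-up time as the offset is ordinary shorthand for its logarithm under a log link, and nothing in the SAP says otherwise.

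**Conclusion.** The point holds conditionally. The measure is mislabelled, the counting rule is open, and the only specified between-arm estimate for adverse events other than eosinophilia and death has an interval whose width is right only if counts happen to vary as Poisson.

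If repeat events count and rates differ between patients, false rejection is about 5% to 37%, under assumed frailty variance 0.25 to 2 and 0.5 to 2 events per patient. The upper end needs frequent, strongly clustered events, as in a composite count. With no extra variation, or for rare event types, the effect is negligible. If only first events count, the interval is too wide, with coverage of 96% to 99%. This is a secondary safety analysis in an exploratory trial, so the matter is worth correcting but does not threaten the primary result.

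**What to change.** Amend SAP 2.2.2 and 5.3.2 to:

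- state whether repeat events in one patient count, and how an episode that fits several listed categories is counted;
- report, by arm, the proportion of patients with at least one event as the cumulative incidence, with a risk difference and 95% CI;
- call events per person-time an incidence rate;
- estimate its rate ratio with a patient-level robust or Pearson-scaled variance and a t reference.

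The cost is a few sentences and a procedure option, with no new data. Rate-ratio intervals become about 1.0 to 2.4 times as wide, depending on dispersion. The protocol reports 60-day findings from the parent trial, so if these adverse event data have already been analysed, the revised analysis should be dated and labelled post hoc.
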